10. STATISTICAL METHODOLOGY

10.1 General

Data listings will be provided for all data that is databased. Summary statistics and statistical analysis will only be presented for data where detailed in this SAP. For continuous data, summary statistics will include the arithmetic mean, arithmetic standard deviation (SD), median, min, max and n; for log-normal data (e.g. the PK parameters: AUCs and maximum observed drug concentration [C_{max}]) the geometric mean and geometric coefficient of variation will also be presented. For categorical data, frequency count and percentages will be presented. Data listings will be provided for all patients up to the point of withdrawal, with any patients excluded from the relevant population highlighted. Summary statistics and statistical analyses will generally only be performed for patients included in the relevant analysis population. For the calculation of summary statistics and statistical analysis, unrounded data will be used.

Mean change from baseline is the mean of all individual patients' change from baseline values. Each individual change from baseline will be calculated by subtracting the individual patient's baseline value from the value at the timepoint. The individual patient's change from baseline

CONFIDENTIAL

Labcorp Study: 1001215-8442739 Protocol Reference: I8R-MC-IGBO

values will be used to calculate the mean change from baseline using a SAS procedure such as Proc Univariate.

Data analysis will be performed using SAS® Version 9.4 or greater.

10.2 Demographics and Patient Disposition

Patient disposition will be listed. The demographic variables age, sex, race, ethnicity, country of enrolment, site ID, body weight, height, screening glycated hemoglobin, and duration of T1D will be summarized and listed. All other demographic variables will be listed only.

10.3 Pharmacokinetic Assessment

10.3.1 Pharmacokinetic Analysis

Glucagon concentration data after NG administration will be analyzed using a population PK approach via nonlinear mixed-effects modeling with the NONMEM software due to limited number of PK samples collected in this study. Model-estimated population PK parameters will be reported. Additional population PK analysis may be performed by combining data from this study with data from other NG studies.

Evaluable PK outcome is defined as having at least 1 postbaseline measure.

Pharmacokinetic concentrations of plasma glucagon by timepoint will be summarized by descriptive statistics and listed. Mean and individual concentration over time plots will also be produced.

Derivation of the PK parameters will be done by Eli Lilly and Company. Eli Lilly and Company will also be responsible for all PK parameter TFLs.

10.3.2 Pharmacokinetic Statistical Methodology

No inferential statistical analyses are planned

10.4 Pharmacodynamic Assessment

10.4.1 Pharmacodynamic Analysis

Due to limited number of PG measurements (5 time points) from the glucose analyzer, a limited number of PD parameters will be estimated. The primary PD parameter is change from baseline of BG_{max} . In addition, other PG parameters, AUC and TBG_{max} , may also be estimated. Actual sampling times will be used for all calculations.

PG AUC will be calculated using the trapezoidal rule. If the first (predose) or last (90 minutes) timepoints are missing, an AUC will not be derived.

Baseline PG concentrations will be calculated from samples obtained immediately prior to glucagon dosing (e.g., predose).

CONFIDENTIAL

Other PD parameters of PG may be calculated if required.

Derivation of the PD parameters will be done by Labcorp. Labcorp will also be responsible for all PD TFLs.

10.4.2 Pharmacodynamic Statistical Methodology

The PG PD parameters, as well as the change from baseline for BG_{max}, where baseline is defined as Day 1 Predose, will be summarized and listed.

Individual concentrations of PG, together with changes from baseline (predose), will also be summarized by timepoint using descriptive statistics and listed. Mean, mean changes from baseline, and individual concentration over time plots will be produced.

No inferential statistical analyses are planned

10.5 Efficacy Assessment

Plasma glucose levels will be measured prior to the administration of glucagon, as well as at various time points after administration and will be used to assess the efficacy of NG.

Efficacy of NG will be assessed in terms of "treatment success", in which treatment success is defined as an increase of PG \geq 20 mg/dL (1.11 mmol/L) from baseline within 30 minutes postdose. The proportion of patients achieving treatment success will be calculated, summarized, and listed. Rescued patients, data after the rescue would be excluded from the analysis, see Section 10.6.2 for further information on rescued patients.

The time to treatment success will be summarized and listed.

A Kaplan-Meier curve will be constructed for the time-to-achieve treatment success.

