8.6. Pharmacodynamics

At the times specified in the SoA, blood samples will be collected for use in a study-approved rapid glucose analyzer (YSI or equivalent) to determine the plasma concentrations of glucose.

Instructions for the collection and handling of blood samples will be provided by the sponsor. The actual date and time (24-hour clock time) of each sampling will be recorded.

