3. INTRODUCTION

This SAP has been developed after review of the Clinical Study Protocol (final version dated 19 March 2021).

This SAP describes the planned analysis of the safety, tolerability, pharmacokinetic (PK), and pharmacodynamic (PD) data from this study. A detailed description of the planned TFLs to be presented in the clinical study report (CSR) is provided in the accompanying TFL shell document.

The intent of this document is to provide guidance for the statistical and PK analyses of data. In general, the analyses are based on information from the protocol, unless they have been modified by agreement with Eli Lilly and Company. A limited amount of information concerning this study (e.g., objectives, study design) is given to help the reader's interpretation. For open-label studies, this SAP must be signed off prior to first patient visit for this study. When the SAP and TFL shells are agreed upon and finalized, they will serve as the template for this study's CSR.

This SAP supersedes the statistical considerations identified in the protocol; where considerations are substantially different, they will be so identified. If additional analyses are required to supplement the planned analyses described in this SAP, they may be performed and will be identified in the CSR. Any substantial deviations from this SAP will be agreed upon with Eli Lilly and Company and identified in the CSR. Any minor deviations from the TFLs may not be documented in the CSR.

This SAP is written with consideration of the recommendations outlined in the International Conference on Harmonisation (ICH) E9 Guideline entitled Guidance for Industry: Statistical Principles for Clinical Trials¹ and the ICH E3 Guideline entitled Guidance for Industry: Structure and Content of Clinical Study Reports².

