8. SAMPLE SIZE JUSTIFICATION

At least 9 patients with an approximate maximum of 20 may be enrolled so that 6 evaluable patients complete the study.

Labcorp Study: 1001215-8442739 Protocol Reference: I8R-MC-IGBO

The sample size is customary for Phase 1 studies evaluating safety, tolerability, PD, and PK, and is not powered on the basis of statistical hypothesis testing.

The sample size assumes a 33% dropout rate.

Patients who are enrolled but not administered treatment may be replaced to ensure that enough patients may complete the study. Patients that do not have at least 1 PD postbaseline measure may also be replaced.

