9. DEFINITION OF ANALYSIS POPULATIONS

The "Efficacy" population will consist of all patients who received at least one dose of NG, and have baseline and at least 1 postbaseline PG measure within 30 minutes after dose administration. For rescued patients, data after the rescue would be excluded from the analysis.

The "Safety" population will consist of all patients who received at least one dose of NG, whether or not they complete all protocol requirements.

The "Pharmacokinetic" population will consist of all patients who received at least one dose of NG and have evaluable PK data. For rescued patients, data after the rescue would be excluded from the analysis.

The "Pharmacodynamic" population will consist of all patients who received at least one dose of NG and have evaluable PD data. For rescued patients, data after the rescue would be excluded from the analysis.

All protocol deviations that occur during the study will be considered for their severity/impact and will be taken into consideration when patients are assigned to analysis populations.

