10.6.8 Safety and Tolerability Statistical Methodology

No inferential statistical analyses are planned.

11. **INTERIM ANALYSES**

After 3 patients have completed the study, patient enrollment will be paused and an interim analysis will be conducted, evaluating the data relating to the primary and secondary objectives

After this interim analysis, if there are no clinically significant safety concerns, study enrollment will resume.

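### Does the SAP need a time window because the 30 min glucose sample falls exactly on the 30-minute success limit?

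*SAP*

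**What the plan says.** The PD row of the Schedule of Activities (Protocol 1.3) places PG samples at predose and at 10, 30, 60 and 90 min after nasal glucagon. Treatment success in SAP 10.5 is a PG rise of at least 20 mg/dL "from baseline within 30 minutes postdose. The proportion of patients achieving treatment success will be calculated, summarized, and listed". To enter the Efficacy population under SAP 9, a child must "have baseline and at least 1 postbaseline PG measure within 30 minutes after dose administration". Neither section gives a sampling window.

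The timing rule is in the PD section, SAP 10.4.1: "Actual sampling times will be used for all calculations". Protocol 9.4.2.1.1 has the same rule. Protocol 8.6 supplies the data for it: "The actual date and time (24-hour clock time) of each sampling will be recorded". Protocol 8.1, 9.4 and 9.4.2.1.2 each describe efficacy as resting on the PD data. Protocol 9.4.3 leaves the efficacy details to the SAP.

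For reporting, SAP 10.4.2 says: "Individual concentrations of PG, together with changes from baseline (predose), will also be summarized by timepoint using descriptive statistics and listed". SAP 10.5 adds a listing and summary of time to success, and a Kaplan-Meier curve.

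**The concern.** Only two scheduled samples can show success, and the later one is due at the moment the period closes. Any delay in drawing blood from a child under 4 puts that sample past the limit. The actual-time rule is not repeated in SAP 9 or 10.5, so two conventions seem possible: actual elapsed time, or the scheduled timepoint with some allowance. They can classify the same child differently.

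Three features appear to make this worse.

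- The by-timepoint table could show a rise of 20 mg/dL or more at 30 min for a child whom the efficacy table counts as a failure.
- SAP 8 states: "Patients that do not have at least 1 PD postbaseline measure may also be replaced". A child who leaves the Efficacy population because of a late draw still has a postbaseline PD measure, so this provision would not reach that child.
- Bedside glucose readings are not databased (SAP 10.6.2), so they cannot fill the gap.

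SAP 3 says: "For open-label studies, this SAP must be signed off prior to first patient visit for this study". SAP 11 says that after three patients "an interim analysis will be conducted, evaluating the data relating to the primary and secondary objectives". PG is secondary-endpoint data, so a convention fixed after that point would be chosen with the responses in view.

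**Working it through.** **Denominators.** The plan wants 6 evaluable children at 33% dropout: 6 / (1 − 0.33) = 8.96, rounded up to 9. This reproduces the stated minimum of 9. The stated approximate maximum is 20. I use n = 6, 9 and 20.

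**When a late 30 min draw matters, under actual time.**

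| 10 min sample | Late 30 min sample | Result |
|---|---|---|
| rise ≥20 mg/dL | any | success, unaffected |
| rise <20 mg/dL | rise <20 mg/dL | failure under either convention |
| rise <20 mg/dL | rise ≥20 mg/dL | failure under actual time, success under a nominal window |
| missing | any | child leaves the Efficacy population under actual time, stays under a nominal window |

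Only the last two rows depend on the convention.

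**Weight of one child.** Reclassifying one success moves the proportion by 100/n points:

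- n = 6: 6/6 = 100% to 5/6 = 83.3%, or 16.7 points
- n = 9: 9/9 = 100% to 8/9 = 88.9%, or 11.1 points
- n = 20: 20/20 = 100% to 19/20 = 95.0%, or 5.0 points

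If a child instead leaves a population of 6, a departing non-responder turns 5/6 = 83.3% into 5/5 = 100%. A departing responder, with one other child failing, turns 5/6 into 4/5 = 80.0%. The direction is therefore not fixed.

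**Precision of the proportion.** The SAP plans no confidence interval. As illustration only, exact 95% intervals are 54.1% to 100% for 6/6 and 35.9% to 99.6% for 5/6. They overlap over most of their length.

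**Likelihood.** The documents give neither the chance q that the 30 min draw is late nor the share s of children who first reach +20 mg/dL at that sample. Taking the two as independent, the chance that at least one child's status turns on the rule is 1 − (1 − qs)^n. At n = 6:

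- q = s = 0.10: 1 − 0.99^6 = 6%
- q = s = 0.25: 1 − 0.9375^6 = 32%
- q = s = 0.50: 1 − 0.75^6 = 82%

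The range is too wide to show that the event is either likely or rare.

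**Which clock applies.** SAP 10.4.1 extends actual times to every calculation on the analyzer PG data. Success is calculated from those same samples, and three protocol sections tie efficacy to PD. Read together, actual time decides and the limit is 30 minutes, which gives each child one classification. Protocol 8.6 mentions no seconds. If times are held in whole minutes, the question starts at a recorded 31 min.

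**The case for a change.** The best argument for a change is that it costs one sentence. The protocol handed these details to the SAP, and SAP 10.5 largely restates the protocol's definition. The actual-time rule sits under a PD heading, so its reach into efficacy is an inference. If it does reach there, strict actual time with no allowance is what excludes a 31-minute draw. Such a draw is plausible: at 30 min the site takes a 2 mL PK sample as well as the PD sample from a very young child.

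It stands that neither document states a tolerance and that one child carries visible weight at n = 6. But a strict limit is not an ambiguous one, and the 1/n weight applies to any responder rule at this sample size. Choosing between the clocks is a trade-off. Actual time drops a rise seen just after 30 min; a nominal window may credit a rise first reached after it. Asking the SAP to name either convention, without a reason to prefer one, adds documentation but not a better analysis.

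The supporting points are weak. A by-timepoint summary and a time-limited responder count answer different questions, so they do not conflict when they differ. The replacement sentence concerns PD data, and enrolment has room up to about 20. The interim analysis covers primary and secondary objectives, not the success proportion. The PG values would be visible there, but no inferential test is planned that a later convention could distort.

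**Conclusion.** No change to the plan is needed. This is a gap in wording that analysts would fill sensibly, most naturally by applying the actual-time rule of SAP 10.4.1 to both the Efficacy population and the success count. What could move is one exploratory, descriptive proportion, by 16.7 points per reclassified child at n = 6 and 5.0 at n = 20, together with the time-to-success displays that share its definition. Individual PG values and times to success are listed, so a reader could find an affected child and recount. The primary safety endpoint, the secondary PD and PK results and the sample size are untouched.

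This conclusion assumes that efficacy inherits the PD timing rule, which the text supports but does not state. The TFL shell document (SAP 3) and the sponsor's sampling instructions (Protocol 8.6) were not available and may already contain a window. The frequency of late draws is unknown.

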10.6 Safety and Tolerability Assessments

10.6.1 Adverse events

Where changes in severity are recorded in the Case Report Form (CRF), each separate severity of the adverse event (AE) will be reported in the listings, only the most severe will be used in the summary tables. A pre-existing condition is defined as an AE that starts before the patient has provided written informed consent and is ongoing at consent. A non-TEAE is defined as an AE which starts after informed consent but prior to dosing. A TEAE is defined as an AE which occurs postdose or which is present prior to dosing and becomes more severe postdose.

All AEs will be listed. Treatment-emergent AEs will be summarized by severity and relationship to the study drug. The frequency (the number of AEs, the number of patients experiencing an AE and the percentage of patients experiencing an AE) of TEAEs will be summarized by Medical Dictionary for Regulatory Activities (MedDRA) version 24.0 system organ class and preferred term. The summary and frequency AE tables will be presented for all causalities and those considered related to the study drug by the investigator. Any serious AEs will be listed.

CONFIDENTIAL Labcorp Study: 1001215-8442739 Protocol Reference: I8R-MC-IGBO

Nasal/respiratory and anosmia AEs (see Appendix 2) will be summarized.

Discontinuations due to AEs will be listed.

10.6.2 Glucose Monitoring and Hypoglycemia

At baseline, during, and after dosing, blood glucose (BG) levels will be measured at the bedside for safety monitoring using an approved point-of-care glucometer. The bedside glucose measurements will be performed for safety monitoring only and will not be databased.

Severe hypoglycemica in children events will be listed and summarized. Severe hypoglycemia in children is defined³ as follows:

Severe hypoglycaemia in children: because children have limited ability to detect and/or self-treat hypoglycemia, severe hypoglycemia in children is an event in which children have severe cognitive impairment, and require external assistance, are semiconscious or unconscious, or in coma with or without convulsions, and requires another person to actively administer carbohydrates, glucagon, or take other corrective action

The determination of a hypoglycemic event as an episode of severe hypoglycemia, as defined above, will be made by the investigator based on the medical need of the patient to have had hypoglycemia-induced cognitive dysfunction and is not predicated on the report of a patient simply having received assistance.

Further information on patients that experience a hypoglycemic event will be collected using a hypoglycaemia event CRF form, this data will be listed and summarized.

A glucose infusion alternative glucagon therapy, or oral carbohydrate may be used for rescue treatment if a patient's BG level is declining rapidly, or their symptoms become consistent with progression to clinically significant or severe hypoglycemia. A separate listing will be presented for the use of rescue medication used for severe hypoglycaemia.

The following steps will be taken based on the patient's baseline BG level:

- If BG < 70 mg/dL, the investigator will determine whether to proceed with dosing or to use rescue treatment.
- If BG < 54 mg/dL (clinically significant hypoglycemia [Level 2]), site will halt study drug procedure and use rescue therapy to raise BG level. Such patients' visits may be rescheduled for a subsequent visit

10.6.3 Concomitant medication

Concomitant medication will be coded using the WHO drug dictionary (Version March 2021). Concomitant medication will be listed.

CONFIDENTIAL Protocol Reference: I8R-MC-IGBO Labcorp Study: 1001215-8442739

10.6.4 Vital signs

Vital signs data will be listed for individual patients.

Changes from baseline (Day 1 predose) will be calculated for vital signs.

10.6.5 Hepatic Monitoring

If a patient experiences elevated laboratory parameters, as detailed in Section 10.4 of the protocol, additional tests will be performed to confirm the abnormality. Additional safety data may be collected if required, as defined in the protocol. Where applicable, the following will be presented.

The patients' liver disease history and associated person liver disease history data will be listed. Any concomitant medications that have potential for hepatotoxicity, including acetaminophen will be listed. Results from any hepatic monitoring procedures, such as a magnetic resonance elastography scan, and biopsy assessments will be listed, if performed.

Hepatic risk factor assessment data will be listed. Liver related signs and symptoms data will be summarized by treatment and listed. Alcohol and recreational drug use data will also be listed.

All hepatic chemistry, hematology, coagulation, and serology data will be listed. Values outside the reference ranges will be flagged on the individual patient data listings.

10.6.6 Nasal Inspection

AEs found during Nasal inspection will be summarized and listed by pre-dose and 90 min postdose respectively. TEAEs found during nasal inspection will also be summarized and listed.

10.6.7 Other assessments

All other safety assessments not detailed in this section will be listed but not summarized or statistically analyzed.

10.6.8 Safety and Tolerability Statistical Methodology

No inferential statistical analyses are planned.

11. **INTERIM ANALYSES**

After 3 patients have completed the study, patient enrollment will be paused and an interim analysis will be conducted, evaluating the data relating to the primary and secondary objectives

After this interim analysis, if there are no clinically significant safety concerns, study enrollment will resume.

12. CHANGES FROM THE PROTOCOL SPECIFIED STATISTICAL ANALYSES

There were no changes from the protocol specified statistical analyses.

Statistical Analysis Plan CONFIDENTIAL Labcorp Study: 1001215-8442739 Protocol Reference: I8R-MC-IGBO

14. DATA PRESENTATION

14.1 Derived Parameters

Individual derived parameters (e.g. PK parameters) and appropriate summary statistics will be reported to three significant figures. Observed concentration data, e.g. BG_{max} , should be reported as received. Observed time data, e.g. TBG_{max} , should be reported as received. N and percentage values should be reported as whole numbers. Median values should be treated as an observed parameter and reported to the same number of decimal places as minimum and maximum values.

14.2 Missing Data

Missing data will not be displayed in listings.

14.3 Insufficient Data for Presentation

Some of the TFLs may not have sufficient numbers of patients or data for presentation. If this occurs, the blank TFL shell will be presented with a message printed in the center of the table, such as, "No serious adverse events occurred for this study."

Statistical Analysis Plan CONFIDENTIAL Labcorp Study: 1001215-8442739 Protocol Reference: I8R-MC-IGBO

15. APPENDICES

Appendix 1: Document History

Status and Version	Date of Change	Summary/Reason for Changes
Final Version 1.0	NA	NA; the first version.

NA = not applicable

Statistical Analysis Plan CONFIDENTIAL Labcorp Study: 1001215-8442739 Protocol Reference: I8R-MC-IGBO

